10.3.3. Definition of Adverse Events of Special Interest

Per the Council for International Organizations of Medical Sciences Cumulative Pharmacovigilance Glossary ([CIOMS VI, 2021](#)), an AESI (serious or non-serious) is one of scientific and medical concern specific to the Sponsor’s product or program, for which ongoing monitoring and rapid communication by the Investigator to the Sponsor may be appropriate. Such events may require further investigation in order to characterize and understand them.

Events Meeting the AESI Definition

Injection Site Reaction

An ISR is characterized by an intense adverse reaction (usually immunologic) developing at the site of an injection after 4 or more hours post-injection. Subcutaneous administration of the study intervention may cause a specific local reaction originating around the injection site, such as erythema, itching, discomfort and pain, and could include more severe manifestations such as ulceration or necrosis.

Potential ISRs will be evaluated and recorded as follows:

Individual signs or symptoms at the injection site with an onset of less than 4 hours from the time of study intervention administration will be recorded as individual AEs (bruising, itching, transient erythema, swelling, etc.) and not as ISRs.

Signs or symptoms at the injection site with a time to onset of 4 or more hours post-injection will be recorded as an ISR if any of the CTCAE criteria for ISR detailed in [Table 7](#) are met. Signs or symptoms at the injection site that occur \geq 4 hours post-injection but are not specified in [Table 7](#) should be recorded as AEs.

Table 7: Grading of Injection Site Reactions, CTCAE v 5.0

Grade 1	Grade 2	Grade 3	Grade 4	Grade 5
Tenderness with or without associated symptoms (e.g., warmth, erythema, itching)	Pain, lipodystrophy; edema; phlebitis	Ulceration or necrosis; severe tissue damage; operative intervention indicated	Life-threatening consequences; urgent intervention indicated	Death

10.3.4. Recording and Follow-up of AEs and/or SAEs

10.3.4.1. AE and SAE Recording

When an AE/SAE occurs, it is the responsibility of the Investigator to review all documentation (e.g., hospital progress notes, laboratory reports, diagnostics reports) related to the event.

The Investigator will then record all relevant AE/SAE information in the eCRF.

It is not acceptable for the Investigator to send photocopies of the participant's medical records to the Sponsor in lieu of completion of the AE/SAE CRF page.

There may be instances when copies of medical records for certain cases are requested by the Sponsor. In this case, all participant identifiers, with the exception of the participant number, will be redacted on the copies of the medical records before submission to the Sponsor.

The Investigator will attempt to establish a diagnosis of the event based on signs, symptoms, and/or other clinical information. Whenever possible, the diagnosis (not the individual signs/symptoms) will be documented as the AE/SAE.

10.3.4.2. Assessment of Intensity

The Investigator will make an assessment of each AE and SAE reported during the study. The grade of each event will be determined using CTCAE v 5.0 criteria.

10.3.4.3. Assessment of Causality

The Investigator is obligated to assess the relationship between study intervention and each occurrence of each AE/SAE.

A “reasonable possibility” of a relationship conveys that there are facts, evidence, and/or arguments to suggest a causal relationship, rather than a relationship cannot be ruled out.

The Investigator will use clinical judgment to determine the relationship. Alternative causes, such as concomitant therapy and other risk factors, as well as the temporal relationship of the event to study intervention administration will be considered and investigated. The Investigator will also consult the Investigator Brochure (IB) and/or Product Information (for marketed products) in his/her assessment.

For each AE/SAE, the Investigator must document in the medical notes that he/she has reviewed the AE/SAE and has provided an assessment of causality.

There may be situations in which an SAE has occurred, and the Investigator has minimal information to include in the initial report. However, it is very important that the Investigator always make an assessment of causality for every event before the initial transmission of the SAE data to SAE Coordinator.

The Investigator may change his/her opinion of causality in light of follow-up information and send a SAE follow-up report with the updated causality assessment.

The causality assessment is one of the criteria used when determining regulatory reporting requirements.

The following definitions will be used in assessing causality:

- **Not Related:** Event for which sufficient evidence exists to conclude that the etiology is unrelated to study intervention.
- **Possibly Related:** There is some temporal relationship between the event and the administration of the study intervention, and the event is unlikely to be explained by the participant’s medical condition or other therapies.
- **Probably Related:** The temporal relationship between the event and administration of the study intervention is suggestive and the event is unlikely explained by the participant’s medical condition or other therapies.
- **Definitely Related:** The event follows reasonable temporal sequence from administration of the study intervention, follows a known or suspected response pattern to the study intervention, is confirmed by improvement upon stopping the study intervention, and reappears upon repeated exposure, if that occurs.

10.3.4.4. Follow-up of AEs and SAEs

The Investigator is obligated to perform or arrange for the conduct of supplemental measurements and/or evaluations as medically indicated or as requested by the Sponsor to elucidate the nature and/or causality of the AE or SAE as fully as possible. This may include additional laboratory tests or investigations, histopathological examinations, or consultation with other health care professionals.

If a participant dies during participation in the study or during a recognized follow-up period, the Investigator will provide the Sponsor with a copy of any post-mortem findings including histopathology.

New or updated information will be recorded in the originally completed CRF.

The Investigator will submit any updated SAE data to the Sponsor within 24 hours of receipt of the information.

10.3.5. Reporting of SAEs

Facsimile or electronic transmission of the SAE Report Form is the preferred method to transmit this information to the SAE coordinator.

In rare circumstances and in the absence of facsimile equipment, notification by telephone is acceptable with a copy of the SAE data collection tool sent by overnight mail or courier service.

Initial notification via telephone does not replace the need for the Investigator to complete and sign the SAE Report Form within the designated reporting time frames.

Contacts for SAE reporting can be found on the [Medical Monitor and Pharmacovigilance Contact Information](#) page.

10.4. Contraceptive Guidance and Collection of Pregnancy Information

10.4.1. Definitions

Woman of Childbearing Potential (WOCBP)

A woman is considered fertile following menarche and until becoming post-menopausal unless permanently sterile (see below).

If fertility is unclear (e.g., amenorrhea in athletes) and a menstrual cycle cannot be confirmed before administration of study intervention, additional evaluation should be considered.

Women in the following categories are not considered WOCBP

1. Premenarchal
2. Premenopausal with one of the following:
 - a. Documented hysterectomy
 - b. Documented bilateral salpingectomy
 - c. Documented bilateral oophorectomy

For individuals with permanent infertility due to an alternate medical cause other than the above, (e.g., müllerian agenesis, androgen insensitivity), Investigator discretion should be applied to determining study entry.

Note: Documentation can come from the site personnel's: review of the participant's medical records, medical examination, or medical history interview.

3. Postmenopausal

- a. A postmenopausal state is defined as no menses for 12 months without an alternative medical cause.

A high follicle stimulating hormone (FSH) level in the postmenopausal range may be used to confirm a postmenopausal state in women not using hormonal contraception or hormonal replacement therapy (HRT). However, in the absence of 12 months of amenorrhea, confirmation with more than one FSH measurement is required.

- b. Participants on HRT and whose menopausal status is in doubt will be required to use one of the non-estrogen hormonal highly effective contraception methods if they wish to continue their HRT during the study. Otherwise, they must discontinue HRT to allow confirmation of postmenopausal status before study enrollment.

10.4.2. Contraception Guidance

Male Participants

Male participants with female partners of childbearing potential are eligible to participate if they agree to ONE of the following from Day 1 through the end of study (EOS) visit:

- Are abstinent from penile-vaginal intercourse as their usual and preferred lifestyle (abstinent on a long-term and persistent basis) and agree to remain abstinent.
- Agree to use a male condom plus partner use of a contraceptive method with a failure rate of < 1% per year as described in [Table 8](#) when having penile-vaginal intercourse with a WOCBP who is not currently pregnant.

Male participants must refrain from donating sperm for the duration of the study and following the last dose of study intervention for at least 24 weeks.

Male participants with a pregnant or breastfeeding partner must agree to remain abstinent from penile-vaginal intercourse or use a male condom during each episode of penile penetration during the protocol-defined time frame.

Female Participants

Female participants of childbearing potential are eligible to participate if they agree to use a highly effective method of contraception consistently and correctly as described in [Table 8](#).

Table 8: Highly Effective Contraceptive Methods

Highly Effective Contraceptive Methods That Are User Dependent ^a (Failure rate of <1% per year when used consistently and correctly)
Combined (estrogen- and progestogen-containing) hormonal contraception associated with inhibition of ovulation 
 • Oral • Intravaginal • Transdermal
Progestogen-only hormonal contraception associated with inhibition of ovulation 
 • Oral • Injectable
Sexual abstinence 
Sexual abstinence is considered a highly effective method only if defined as refraining from heterosexual intercourse during the entire period of risk associated with the study intervention. The reliability of sexual abstinence needs to be evaluated in relation to the duration of the study and the preferred and usual lifestyle of the participant.

Highly Effective Methods That Are User Independent ^a

 • Implantable progestogen-only hormonal contraception associated with inhibition of ovulation • Intrauterine device (IUD) • Intrauterine hormone-releasing system (IUS) • Bilateral tubal occlusion • Vasectomized partner 
A vasectomized partner is a highly effective contraception method provided that the partner is the sole male sexual partner of the WOCBP, and the absence of sperm has been confirmed. If not, an additional highly effective method of contraception should be used.

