2.2.2. Risk Assessment

Potential Risk of Clinical Significance	Summary of Data/ Rationale for Risk	Mitigation Strategy
Study Intervention: DCR-AUD		
Injection site reactions	Subcutaneous administration of the study intervention may cause a specific local reaction originating around the injection site, such as erythema, itching, discomfort, and pain.	Most ISRs are mild and self-limiting. Participants will be monitored for the development of ISRs (Section 10.3.3)
Potential reproductive effects	In a preliminary EFD study in rabbits with daily SC dosing, maternal toxicity in dams and embryofetal effects were observed at all dose levels. The human relevance of these preliminary nonclinical reproductive studies is unclear.	All participants of childbearing potential are required to practice highly effective contraception consistently throughout the study and for 24 weeks after the last dose of study intervention (Section 10.4).
Severe symptoms associated with acetaldehyde accumulation following consumption of alcohol	In sufficient amounts, acetaldehyde accumulation is associated with unpleasant effects, including flushing, headache, lightheadedness, palpitations, nausea, and vomiting. More severe reactions to acetaldehyde accumulation can include copious vomiting, sweating, chest pain, palpitation, dyspnea, hypotension, syncope, marked uneasiness, weakness, vertigo, blurred vision, and confusion.	If significant or severe adverse symptoms occur in ≥ 3 participants treated with DCR-AUD during the trial, additional DCR-AUD dosing (if scheduled) and subsequent EIAs will be discontinued. In the event this occurs, all study participants will be advised to avoid alcohol for the entire study observation period.
Suicidal ideation or behavior (SIB)	Patients diagnosed with AUD may be at risk for SIB. Because DCR-AUD is being developed for the treatment of AUD, HV will be screened and monitored for the presence or emergence of SIB while on study.	There is no evidence to suggest that HV exposed to DCR-AUD are at risk for SIB, however, all participants will be monitored for the emergence of SIB via the C-SSRS at regular intervals throughout the study (Section 8.2.5.1).
Study Procedures		

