5. STUDY POPULATION

Sixteen participants are planned to be enrolled in this study: 12 will receive DCR-AUD and 4 will receive placebo.

Protocol waivers or exemptions are not allowed. Participants may undergo rescreening one time at the discretion of the Investigator or Sponsor ([Section 5.4](#))

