5.1. Inclusion Criteria

Participants are eligible to be included in the study only if all the following criteria apply.

Age

1. 21 to 65 years, inclusive, at the time of signing informed consent.

Type of Participant and Disease Characteristics

2. Overtly healthy volunteers, as determined by medical evaluation including medical history, physical examination, and laboratory testing.
3. No diagnosis of AUD within the preceding 12 months per Diagnostic and Statistical Manual of Mental Disorders (DSM-5).
4. Social drinkers who consume, on average, 5 to 20 drinks per week for men or 5 to 14 drinks per week for women over the 4 weeks prior to Screening, and not more than 8 drinks in a single day.
5. No evidence of overt or sub-clinical hepatic pathology, as manifest by serologic tests demonstrating hepatic inflammation or compromised hepatic synthetic function (i.e., AST, ALT, GGT, total bilirubin < 1.5 times the ULN at Screening and Day -1).
6. eGFR \geq 60 mL/min/1.73 m² at Screening.
7. No history of significant adverse reaction(s) to alcohol. Participant should be expected to tolerate the amount of alcohol administered during EIAs.
8. Willing to participate in up to 10 EIAs.
9. Has a negative test for SARS-CoV-2 infection on Day -1.
10. Systolic BP in the range of 80 to 140 mmHg and diastolic BP in the range of 50 to 95 mmHg at Screening. If out of range, BP may be repeated once at the discretion of the Investigator.

Sex and Contraceptive Requirements

11. Male or female
 - Male participants with partners of childbearing potential must agree to use contraception from Screening through at least 24 weeks after the last dose of study intervention and refrain from donating sperm during this period (see [Section 10.4](#)).
 - Female participants may not be pregnant or breastfeeding, and at least one of the following conditions must apply:
 - Is not a woman of childbearing potential (WOCBP) **or**

- If a WOCBP, must agree to follow the contraceptive guidance (see [Section 10.4](#)), beginning at consent and the first Screening visit and for at least 24 weeks after the last dose of study intervention.

Weight

12. BMI within the range 18.0 to 32.0 kg/m² (inclusive).

Informed Consent

13. Capable of giving signed informed consent, which includes compliance with the requirements and restrictions listed in the ICF and in this protocol.

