8.3.5. Pregnancy

Details of all pregnancies in female participants and female partners of male participants will be collected after the start of study intervention and until 24 weeks after the last dose.

If a pregnancy is reported, the Investigator should inform the Sponsor within 24 hours of learning of the pregnancy and should follow the procedures outlined in [Section 10.4.3](#).

While pregnancy itself is not considered to be an AE or SAE, any pregnancy complication or elective termination of a pregnancy for medical reasons will be reported as an AE or SAE. Abnormal pregnancy outcomes (e.g., spontaneous abortion, fetal death, stillbirth, congenital anomalies, ectopic pregnancy) are considered SAEs.

The participant or pregnant partner will be followed to determine the outcome of the pregnancy. The Investigator will collect follow-up information on the participant or pregnant partner and the neonate, and the information will be forwarded to the Sponsor.

Any post-study pregnancy-related SAE considered reasonably related to the study intervention by the Investigator will be reported to the Sponsor as described in [Section 8.3.4](#). While the Investigator is not obligated to actively seek this information in former study participants, he or she may learn of an SAE through spontaneous reporting.

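### Section 10.4.2 ends male contraception at the EOS visit, 56 days before the period in inclusion criterion 11 for a fully dosed man; partner-pregnancy collection in 10.4.3.1 is likewise narrower than in 8.3.5

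*Protocol*

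**What the plan says.** Two parts of the protocol give a contraception period for the same men.

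- **Section 5.1, inclusion criterion 11.** A man whose partner could become pregnant "must agree to use contraception from Screening through at least 24 weeks after the last dose of study intervention"; sperm donation is barred for the same time. The criterion refers to Section 10.4 for detail. Section 5.1 opens with "Participants are eligible to be included in the study only if all the following criteria apply", and Section 5 adds "Protocol waivers or exemptions are not allowed".
- **Section 10.4.2.** The same men are eligible if they "agree to ONE of the following from Day 1 through the end of study (EOS) visit". The choices are abstinence, or a condom plus a highly effective partner method. A few lines later comes a sperm-donation rule, under which every man is to "refrain from donating sperm for the duration of the study and following the last dose of study intervention for at least 24 weeks". Men whose partner is pregnant or breastfeeding must be abstinent or "use a male condom during each episode of penile penetration during the protocol-defined time frame"; no dates are attached.

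The risk table in Section 2.2.2 cites Section 10.4 for the requirement that participants of childbearing potential "practice highly effective contraception consistently throughout the study and for 24 weeks after the last dose of study intervention".

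Two sections cover partner pregnancies. Section 8.3.5 applies to women in the trial and also to the men's partners: details of pregnancies in "female partners of male participants will be collected after the start of study intervention and until 24 weeks after the last dose". It points to Section 10.4.3 for the procedure. Section 10.4.3.1 covers only partner pregnancies that begin while the man is in the study, and only for men who receive DCR-AUD.

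**The concern.** A reader who follows the cross-reference from criterion 11 arrives at a shorter period than the criterion itself. Section 10.4.2 is also phrased as an eligibility condition, so the protocol states two eligibility periods for one group. It differs from its own sperm-donation rule too, and gives no reason for the difference.

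Criterion 11 asks only for contraception. The acceptable methods for men appear only in 10.4.2, tied to the shorter period, so the method for the remaining weeks is not spelled out. The undated time frame for men with a pregnant or breastfeeding partner can be read as either period.

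In practice, a site that counsels men from 10.4.2 would release them before the sponsor's own safety period ends. Apart from the discretionary Day 197 visit, no study visit follows EOS at which this could be corrected. A site that works from 10.4.3.1 alone could also fail to record a partner pregnancy that 8.3.5 requires.

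**Working it through.** **Inputs**

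- Doses on Days 1, 29 and 57 (Section 1.1.3).
- EOS on Day 169 (Section 4.4).
- Optional follow-up visit on Day 197 (Section 4.1).
- Required cover of 24 weeks = 168 days after the last dose (Section 5.1, criterion 11).

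**The plan's own figure.** Day 1 + 168 = Day 169, which matches the stated EOS. EOS is therefore 24 weeks after the *first* dose. From the last scheduled dose it is (169 − 57)/7 = 16 weeks.

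**Shortfall for men followed to Day 169.** With last dose on day D, the gap is D + 168 − 169. Days are nominal.

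| Last dose | 24 weeks after it | Gap after EOS |
|---|---|---|
| Day 57 | Day 225 | 56 days |
| Day 29 | Day 197 | 28 days |
| Day 1 | Day 169 | 0 days |

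**Sensitivity**

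- *Visit windows.* Take the Day 57 dose as ±2 days and assume an EOS window of ±7 days. The gap then runs from (55 + 168) − 176 = 47 to (59 + 168) − 162 = 65 days. With an assumed ±3 days it runs from 223 − 172 = 51 to 227 − 166 = 61 days.
- *Day 197 visit.* If this were counted as end of study, the gap after a Day 57 dose would be 225 − 197 = 28 days.
- *Early termination.* Table 1 has a combined EOS/ET column, but 10.4.2 does not say whether an ET visit counts as the EOS visit. Assuming that it does, the gap is D + 168 − T for termination on day T. For a Day 57 last dose it lies between 56 days (T = 169) and 168 days (T = 57). For example, T = 85 gives 225 − 85 = 140 days. The corresponding ranges are 28 to 168 days for a Day 29 last dose and 0 to 168 days for Day 1.

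The start points also differ (Screening against Day 1). That interval precedes any study drug and is not counted.

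**Partner pregnancies, side by side**

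| | Section 8.3.5 | Section 10.4.3.1 |
|---|---|---|
| Ends | 24 weeks after last dose (Day 225 if fully dosed) | When the man leaves the study (Day 169 if he completes without the optional visit) |
| Men covered | All male participants | Only those who receive DCR-AUD |

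The time difference is again 225 − 169 = 56 days. Section 6.3 keeps the Investigator blinded for the duration of the study, and the Investigator is the person told to collect the information. The arm limit therefore cannot be applied at the site without learning the assignment.

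**The case against.** The best defence is that nothing required is missing. All criteria must be met and no waivers are allowed, so a man who agrees only through EOS is not eligible. Section 8.3.5 independently requires partner-pregnancy details to 24 weeks. Section 2.1.2 reports that DCR-A1203 was not genotoxic and calls the human relevance of the rabbit embryofetal findings unclear. The documents show no male-mediated risk. The consent form was not available and may state the longer period. All of this stands. It limits the seriousness of the point, but it does not reconcile the sections.

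Some narrower objections also have force:

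- The early-termination ranges rest on an unstated reading of the EOS visit. The firm figures are 56, 28 and 0 days.
- The risk-table line may refer to women only, so it is supporting text and decides nothing.
- Some sponsor staff are unblinded. A site could collect from every man, as 8.3.5 requires, and leave any arm limit to the sponsor. That workaround is not what 10.4.3.1 says.
- Section 10.4.3.2 has the same time limit for female participants, covering only pregnancies that begin during participation, against 24 weeks after the last dose in 8.3.5. This adds to the point.
- Criterion 11 does not expressly cover men whose partner is pregnant or breastfeeding, so giving them the same period is a reasonable choice rather than pure reconciliation.

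**Conclusion.** The inconsistency is real and should be corrected. For a man who receives all three doses and is followed to Day 169, Section 10.4.2 falls 56 days (8 weeks) short of criterion 11, on nominal days. The shortfall is 28 days after a Day 29 last dose and nil after Day 1 only. Section 10.4.3.1 is narrower than 8.3.5 in both period and population, and its arm limit does not fit the blind. The safety consequence is modest because the longer requirements exist elsewhere and bind. No endpoint, analysis or sample-size consideration is affected.

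**What to change.** - **Section 10.4.2:** replace the Day 1-to-EOS period with Screening through at least 24 weeks after the last dose of study intervention. Put the same dates in place of the undated time frame for men with a pregnant or breastfeeding partner.
- **Section 10.4.3.1:** replace the in-study limit with the 8.3.5 period, from the start of study intervention until 24 weeks after the last dose. Replace the DCR-AUD-only limit with all male participants who receive study intervention, which a blinded site can apply.
- **Section 10.4.3.2:** give female participants the same 8.3.5 period in the same edit, so that the pregnancy sections agree.

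These are wording changes with no new visits or procedures. Section 10.1.1 requires ethics approval before an amendment to the study design is implemented. Under Section 10.1.3, participants would need re-consent if the consent form changes; whether it would have to change cannot be judged from the documents available.
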